2. BACKGROUND

Azithromycin and other antibiotics are being considered for routine use in settings with high burdens of child morbidity and mortality. In Burkina Faso, the under-5 child mortality rate is 110 per 1,000 live births, which is among the highest child mortality rates in the world.¹ The major causes of child mortality in Burkina Faso are infectious: upper respiratory tract infection, diarrhea, and malaria.^{1,2} Furthermore, malnutrition is a major contributor to child mortality and morbidity, with an estimated 35% of children malnourished in rural Burkina Faso.³ Antibiotics may therefore reduce child morbidity and mortality by treating underlying (often subclinical) infections. *We propose to conduct this study in a region of rural Burkina Faso where the burden of child mortality and morbidity is high, and child deaths are attributable to upper respiratory tract infection, diarrhea, malaria, and malnutrition.*

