3.2.1 Sample Size

We will enroll 120 households into the four study arms (30/arm).

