5. ANTHROPOMETRY

Anthropometry will be collected for all children in Study Two at baseline and 4 weeks after the completion of the treatment. We will measure length or height, weight, and MUAC.

Measuring Length and Height

A lightweight measuring board will be used to measure the participant's height to the nearest 0.1 cm. Height will be assessed with a ShorrBoard. Depending on a child's age and ability to stand, measure the child's length or height.

Length: If a child is less than 2 years old, or cannot stand alone, measure recumbent length. A child's length is measured lying down (recumbent).

Height: If a child is able to stand, we will measure standing height.

Procedure

If the child has braids or hair ornaments that will interfere with length/height measurements, remove them if possible. Check that any sandals, shoes, or socks have also been removed.

Whether measuring length or height, the mother/guardian is needed to help with measurements and to soothe and comfort the child. Explain to the mother the reasons for the measurements, and describe the steps in the procedure. Answer any questions she might have. Show her and tell her how she can help you. Explain that it is important to keep the child still and calm to obtain the best measurement.

ShorrBoard Set-Up

- 1) Remove ShorrBoard from bag.
- 2) Stand the ShorrBoard upright. You can step on the base of the board to keep it stable.
- 3) As you face the board, turn the non-removable bolt counterclockwise to release the extension piece. Note: the bolt remains attached to the back of the extension piece – do NOT remove it.
- 4) Slide the extension piece into the top end of the main board and fasten the clasp on the back of the board. Make sure the clasp is fastened properly.
- 5) The auto-lock sliding head/footpiece is stored in the base of the main board and can be moved up and down the length of the measuring board. It should stay in place on its own wherever you position it.
- 6) The measuring board must be placed against a firm surface for standing height (e.g. wall, table, tree, against a vehicle, etc.). Make sure the board is stable. If necessary, place items such as small rocks underneath the height board to stabilize it during the measurement.
- 7) Clean the equipment with alcohol swabs at the beginning of each day.

Note: when you set up the board each day, examine each of the pieces to check for damage.

[figure not shown]
Measure Length

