Antibiotic Resistance and Microbiome in Children Aged 1-59 months in Nouna, Burkina Faso

Manual of Operations and Procedures

NCT number 03187834

Version 1.1 June 2017

Centre de Recherche en Santé de Nouna

University of Heidelberg

Francis I. Proctor Foundation, University of California, San Francisco

Antibiotic resistance and Microbiome in Children Aged 6-59 months in Nouna, Burkina Faso

Statistical Analysis Plan, Version 1.0, June 15 2017

Study Overview

We will randomize 120 households containing 2 or more children aged 6-59 months to one of four study arms: 1) azithromycin, 2) amoxicillin, 3) cotrimoxazole, or 4) placebo. All children will receive 5 days of treatment. Full intervention details can be found in the Manual of Operations and Procedures. Rectal and nasopharyngeal swabs will be collected pre-treatment (baseline) and on Day 9 following the 5 days of treatment. Anthropometric indices (weight, height, and mid-upper arm circumference) will be collected at baseline and Day 35 (one month following treatment completion).

Randomization

The 120 households will be randomized in blocks of size 8 to one of the four treatment arms. In households randomized to treatment, all children aged 6-59 months of age will be treated, with the exception of one random child from within the household who will receive placebo. All children aged 6-59 months in households randomized to placebo will receive placebo. A random treated child from antibiotic arm households will be selected as the sentinel child for outcome assessment, and the untreated child from antibiotic arm households will also receive outcome assessment. Two children will be randomly selected from placebo households for outcome assessment.

Primary Outcome

We will compare diversity across arms at Day 9 and between time points. The primary outcome will be Simpson's index of alpha diversity. We will compare the mean Simpson's index between treatment arms with a t-test. All *P*-values will be calculated via permutation test.

Secondary Outcomes

As a secondary outcome, we will compare Shannon's index (L1 norm) between time points using a t-test. To compare if treatment significantly explains difference between the four treatment groups, we will compare Simpson's index (L1-norm) and Shannon's index (L2-norm) distances using PERMANOVA on bacterial reads.

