To determine if there are differences in nutritional outcomes across treatment arms one month following treatment, we will calculate weight-for-height (WHZ), weight-for-age (WAZ), and height-for-age (HAZ) Z-scores based on 2006 WHO standards. We will compare mean WHZ, WAZ, HAZ, and mid-upper-arm circumference (MUAC) across treatment arms as continuous variables adjusting for baseline anthropometric values using an ANCOVA. We will also compare

the prevalence of stunting (HAZ <-2 SD) and moderate (WHZ <-2 SD) and severe (WHZ <-3 SD) acute malnutrition across study arms with a logistic regression model.

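### The logistic models for stunting and acute malnutrition name no baseline term, although the ANCOVA on the same measures does; the cost is precision, mainly for stunting

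*SAP*

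**What the plan says.** Under Secondary Outcomes, the SAP analyses WHZ, WAZ, HAZ and MUAC as continuous variables, "adjusting for baseline anthropometric values using an ANCOVA". The next sentence turns to "the prevalence of stunting (HAZ <-2 SD) and moderate (WHZ <-2 SD") and to severe wasting (WHZ below -3), and compares "acute malnutrition across study arms with a logistic regression model". It names no covariate.

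The baseline values exist. Protocol section 5 states: "Anthropometry will be collected for all children in Study Two at baseline and 4 weeks after the completion of the treatment". Section 3.2.2 and the schedule in section 3.2.7 place the first measurement before randomisation. The SAP says the measures "will be collected at baseline and Day 35 (one month following treatment completion").

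On size, Protocol section 3.2.1 says "We will enroll 120 households into the four study arms (30/arm"). The SAP adds: "A random treated child from antibiotic arm households will be selected as the sentinel child for outcome assessment". That gives about 30 treated children in each antibiotic arm, and up to 60 children in the placebo arm, where two per household are assessed. Neither document gives an effect size, a power figure, a prevalence by indicator or a baseline/follow-up correlation for these outcomes.

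**The concern.** The binary outcomes are cut-offs of the same HAZ and WHZ, measured on the same children, that the preceding sentence adjusts for baseline. Over about five weeks, much of whether a child is below -2 at follow-up is settled by where that child stood at entry. If baseline is left out, that predictable variation stays in the error term.

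Two things are at stake. First, the stunting comparison may be much less precise than data already in hand would allow. Second, because the sentence does not say whether baseline enters, the analyst could choose the model after seeing the data. The unadjusted binary result could also point a different way from the adjusted ANCOVA on the same children.

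**Working it through.** **Inputs from the documents.** 120 households / 4 arms = 30 per arm, with one treated sentinel child per antibiotic household. Cut-offs are -2 for HAZ, and -2 and -3 for WHZ. The only prevalence figure is in Protocol section 2, "with an estimated 35% of children malnourished in rural Burkina Faso", which is not broken down by indicator.

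**Assumed inputs.** Two-sided 5% test; two arms of 30; children independent; normal HAZ with mean -1.5 and SD 1.2; correlation 0.6 to 0.9; shift 0.3 or 0.5 Z. The implied stunting prevalences are:

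- No shift: Φ((-2 + 1.5)/1.2) = Φ(-0.417) = 33.8%, close to the 35% in the background.
- 0.3 Z shift: Φ((-2 + 1.2)/1.2) = Φ(-0.667) = 25.2%.
- 0.5 Z shift: Φ((-2 + 1.0)/1.2) = Φ(-0.833) = 20.2%.

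The plan has no power figure to reproduce for these outcomes.

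**Stunting.** Simulated power of the likelihood-ratio test for treatment, without and with continuous baseline HAZ:

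| Correlation | 0.5 Z: without → with | 0.3 Z: without → with |
|---|---|---|
| 0.6 | 24% → 28% | 12% → 14% |
| 0.8 | 24% → 37% | 12% → 18% |
| 0.9 | 22% → 46% | 14% → 25% |

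A separate simulation with 35% prevalence and a 0.4 SD shift (0.5/1.2 = 0.417 SD, so nearly the same effect) gave 24% → 27%, 22% → 32% and 22% → 45%. A four-arm, 3-df test with one active arm gave 18% → 30% at 0.8 and 18% → 44% at 0.9.

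**Why the gain depends on the correlation.** At 35% prevalence, baseline Z predicts about 23%, 43% and 59% of the variance of follow-up stunting at correlations 0.6, 0.8 and 0.9. Dividing 30 by (1 - share) gives a rough equivalent unadjusted sample per arm:

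- 0.6: 30/0.77 = 39
- 0.8: 30/0.57 = 53
- 0.9: 30/0.41 = 73

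As a check, unadjusted power with 60 per arm was 38% to 41% for the 0.5 Z shift. That lies between the adjusted 37% at correlation 0.8 and 46% at 0.9, as it should.

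**Type I error for stunting.** Unadjusted, it was about 4% to 6%. Adjusted with the plain likelihood-ratio test, it was about 5% to 6% at correlations 0.6 to 0.9 in one simulation and about 8% at 0.9 in another.

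**Moderate acute malnutrition (assumed 10%, so 0.10 × 30 = 3 expected events per arm).** With a 0.4 SD shift, power goes from 17% to 19% at 0.6, 17% to 22% at 0.8 and 15% to 25% at 0.9. The adjusted test's type I error is 9% to 11%, against about 7% unadjusted, so part of the gain is spurious.

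**Severe acute malnutrition (assumed 3%, so 0.03 × 30 = 0.9 expected events per arm).** The adjusted fit separated completely in 38% to 78% of data sets across correlations 0.6 to 0.95 (0.4 SD shift). A run under other assumptions gave about 12% to 23%. Neither is workable.

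**A test that holds its level.** A permutation test on baseline-adjusted logistic residuals (2,000 simulated trials, 30 v 30) had type I error of 4.5% to 5.3% at both 35% and 10% prevalence. For a 0.4 SD shift, permutation power without and with baseline was 14% → 31% (correlation 0.8) and 15% → 40% (0.9) for stunting, and 3% → 13% and 3% → 16% for moderate acute malnutrition. Part of this gain arises because the unadjusted permutation test is coarse and conservative.

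**The case against.** **The plan never says the model is unadjusted.** True: the SAP is short and lists few model terms, so this reading rests on silence. But the silence follows directly on a sentence that does name the adjustment, so the text needs an edit whichever model was meant.

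**A reader might infer that chance imbalance at baseline will produce false treatment effects.** The documents do not support that. Households are randomised, and a valid unadjusted test already allows for chance imbalance; its simulated type I error for stunting stayed near 5%. The loss is precision.

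**A reader might infer that all three binary outcomes lose much of their power and that adding a covariate cures this.** That does not hold either. The gain is modest for moderate acute malnutrition, where the plain adjusted test rejects too often, and there is no usable gain for severe acute malnutrition.

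**The size rests on inputs the plan does not give.** This stands. At correlation 0.6 the gain is 2 to 4 percentage points, and at a 0.3 Z shift power stays at or below 25% under either model.

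**Most of the information is recovered elsewhere.** This also stands. ANCOVA on the continuous score had power 47%, 70% and 93% at correlations 0.6, 0.8 and 0.9 for the 0.4 SD shift, well above the adjusted logistic model. Much of the loss comes from dichotomising. The ANCOVA is already planned and the binary outcomes are secondary, which limits the consequence but does not justify analysing them less precisely than the data allow.

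**Conclusion.** The point holds as one of precision. As written, the logistic models leave out baseline Z-scores that the trial collects and uses one sentence earlier. For stunting, with 30 children per arm and a 0.5 Z shift, adding baseline HAZ is worth about 4 percentage points of power at correlation 0.6, 13 at 0.8 and 24 at 0.9; for a 0.3 Z shift it is worth about 2, 6 and 11. A high correlation for height-for-age over about five weeks is plausible, but it is an assumption, as are the mean, SD and shift.

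The calculations ignore clustering of the two assessed children in a placebo household. Using up to 60 placebo children would change the absolute power but probably not the pattern. The primary outcome, Simpson's index, is unaffected.

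**What to change.** Amend the logistic sentence in the SAP's Secondary Outcomes as follows:

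- Include continuous baseline HAZ in the stunting model and continuous baseline WHZ in the moderate acute malnutrition model.
- Take the P-value from a permutation test or a penalised (Firth) fit, not from the plain likelihood-ratio test. The SAP already uses permutation P-values under Primary Outcome. Permute whole households, in line with the allocation scheme actually used.
- Report the standardised (marginal) risk difference with the odds ratio, because the adjusted odds ratio is conditional on baseline.
- Report severe acute malnutrition as counts and percentages by arm, without an adjusted model.

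No new data are needed. The cost is a few lines in the SAP, a little more programming, and a conditional odds ratio that needs the marginal risk difference beside it. The baseline-adjusted ANCOVA should stay as the more powerful comparison of growth.

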3.2 Study Two: Antibiotic treatment and microbiome changes in children

Study Two is a randomized trial of a short course of antibiotics (azithromycin, co-trimoxazole, or amoxicillin) compared to no treatment. We will assess the effect of a short antibiotic course on intestinal and nasopharyngeal bacterial diversity and will test for antibiotic resistance in the resistome. Households with at least 2 children aged 6-59 months will be randomized in a 1:1:1:1 fashion to one of four study arms: 1) azithromycin, 2) amoxicillin, 3) co-trimoxazole, or 4) no treatment. All children minus one in the household will be treated, and we will assess the indirect effect of antibiotic treatment on the untreated child residing in the household. We will measure changes in microbiome three days following completion of the antibiotic course (primary outcome). During the final sample collection we will also complete a brief survey about the children's health particularly about diarrhea and respiratory infections. Finally, 4 weeks after the completion of the treatment we will evaluate the children's growth by doing anthropometric measurements.

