6. COGNITIVE DEVELOPMENT ASSESSMENT

The Developmental Milestones Checklist (DMC-III) will be used to evaluate the development of motor and language skills in 240 children at baseline in this study. The DMC-III includes three subscales: gross motor, fine motor, and language. The original version of the DMC-III was designed for children aged 3 to 24 months. The updated DMC-III includes additional items to assess children aged 2 to 8 years. The DMC-III requires parent interview for all items and includes optional direct observation of the child for all items. For this study, data collectors will include both parent interview and direct observation for all items where possible.

Materials for observation items:

- Pens
- White paper
- A ball (child-size football/soccer ball)
- A small toy
- Small grains in a box
- A pull-toy
- A color sheet printed with boxes of the following colors : blue, green, yellow, brown, purple, white, grey, orange, red, black, and pink

- 5 coins

Preparing the assessment session for observation items:

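### If severe acute malnutrition is at about 3% or below, at least one arm will probably have no cases, and the planned logistic regression then gives no finite odds ratio for that arm

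*SAP*

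**What the plan says.** The SAP (Secondary Outcomes) plans one type of model for three binary nutrition outcomes one month after treatment: stunting, moderate acute malnutrition, and "severe (WHZ <-3 SD) acute malnutrition across study arms with a logistic regression model". It states no expected prevalence, no rule for an arm without events, and no penalised or exact alternative.

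Protocol Section 3.2.1 gives 120 households, 30 per arm. For the number of children, the SAP (Randomization) says that "A random treated child from antibiotic arm households will be selected as the sentinel child for outcome assessment", that "the untreated child from antibiotic arm households will also receive outcome assessment", and that "Two children will be randomly selected from placebo households for outcome assessment". It does not say which of these children enter the anthropometry comparison. Protocol Section 5 collects anthropometry on all Study Two children.

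The only malnutrition figure is in Protocol Section 2, "with an estimated 35% of children malnourished in rural Burkina Faso". That is malnutrition overall, not the share of children with WHZ below -3.

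The SAP's Primary Outcome paragraph says that all P-values come from a permutation test. It does not give the unit that is permuted, or say whether the sentence extends to the logistic models.

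**The concern.** In a logistic model with arm as the only factor, each log odds ratio is the difference between two observed log odds. An arm with no events has a log odds of minus infinity, so maximum likelihood has no finite solution for a contrast with that arm. If the empty arm is placebo, every contrast with placebo is lost. Severe acute malnutrition is the rarest of the three binary outcomes, because it is a subset of WHZ below -2, and the arms are small.

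At stake is a pre-specified secondary analysis that may give no estimate for one or more comparisons. The analyst would then choose between penalisation, exact methods, pooling arms or dropping the outcome with the counts already in view.

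**Working it through.** **Inputs**

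- Arms: 4, allocated 1:1:1:1 (Protocol Section 3.2).
- Households: 120 / 4 = 30 per arm, as Protocol Section 3.2.1 states.
- Children per arm: 30 if one child per household is used, 60 if both assessed children are used. Protocol Section 6 agrees with two per household, since it plans to assess "development of motor and language skills in 240 children at baseline in this study" and 120 x 2 = 240 = 4 x 60. The natural direct-effect comparison is mixed: 30 treated children in each antibiotic arm against 60 placebo children. If all children in larger households were used, an arm could exceed 60.
- Prevalence p of WHZ below -3: not stated. Assumed range 1% to 10%, equal in all arms.

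**Formulas**, with children taken as independent

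- One arm of n empty: q = (1-p)^n.
- At least one of four equal arms empty: 1 - (1-q)^4.
- Mixed sizes: 1 - (1-(1-p)^30)^3 x (1-(1-p)^60).

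Worked example at p = 2%, n = 30: q = 0.98^30 = 0.545, and 1 - 0.455^4 = 0.957.

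| p | Expected cases per arm, n = 30 / 60 | One given arm empty, n = 30 / 60 | Any arm empty, 30 each | Any arm empty, 30/30/30/60 | Any arm empty, 60 each |
|---|---|---|---|---|---|
| 1% | 0.3 / 0.6 | 0.740 / 0.547 | 0.995 | 0.992 | 0.958 |
| 2% | 0.6 / 1.2 | 0.545 / 0.298 | 0.957 | 0.934 | 0.757 |
| 3% | 0.9 / 1.8 | 0.401 / 0.161 | 0.871 | 0.820 | 0.504 |
| 5% | 1.5 / 3.0 | 0.215 / 0.046 | 0.620 | 0.538 | 0.172 |
| 8% | 2.4 / 4.8 | 0.082 / 0.007 | 0.290 | 0.231 | 0.027 |
| 10% | 3.0 / 6.0 | 0.042 / 0.002 | 0.159 | 0.123 | 0.007 |

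The chance of an empty arm falls to 50% at p = 5.9% (30 each), 5.3% (mixed) and 3.0% (60 each).

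**Sensitivity.** For household pairs, the chance that neither child is a case is (1-p)^2 + ICC x p(1-p), raised to the power 30 for an arm. At p = 2% with 60 per arm, an ICC of 0.05 to 0.20 moves 0.76 to between 0.77 and 0.81. A 10% loss to follow-up (27 and 54 per arm) moves the 50% points to about 6.6% and 3.3%. Referral of wasted children (Protocol Section 8) might lower the one-month rate, by an amount that the documents do not give.

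**What the model does with an empty arm.** Illustrative counts, placebo first, 30 per arm:

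- 1/0/2/1: for the empty arm, fitted log OR about -20 or lower, SE above 10,000, no convergence. The arm with 2 cases is still estimable: ln[(2/28)/(1/29)] = 0.73, SE = sqrt(1/2 + 1/28 + 1/1 + 1/29) = 1.25.
- 0/1/2/1: all three contrasts with placebo diverge.
- In both, the overall likelihood-ratio test still exists (P = 0.42).

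**Permutation.** With 5 cases among 240 children in four arms of 60, 76% of child-level reshuffles leave an arm empty; with 8 cases, 36% do. A permutation test based on an ordinary coefficient or Wald ratio would therefore often break down inside the reshuffles, even if no observed arm is empty. The statistic has to be one that stays finite.

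**The case against.** Several stronger readings are tempting, and the documents do not support them.

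- A reader might infer that an empty arm is the usual result whatever the prevalence. No WHZ below -3 figure is given. Between about 3% and 6% the answer depends on which children are analysed, and above about 6% an empty arm is less likely than not at either size.
- A reader might infer that the analysis would yield nothing usable. An empty antibiotic arm removes only the contrasts with that arm. Losing every placebo contrast needs an empty placebo arm. At 2% that has probability 30% if both assessed placebo children per household are used, and 55% only if one is.
- A reader might infer that the P-values would be meaningless. The SAP names no Wald test, a likelihood-ratio P-value survives an empty arm, and the permutation sentence may be meant to cover this model.
- A reader might extend the problem to stunting and moderate acute malnutrition. If those are at 15% or more (also an assumption), the chance of an empty arm of 30 is 3% or less.

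It is also fair to say that the SAP keeps a baseline-adjusted ANCOVA of WHZ as a continuous variable, which empty cells do not touch, and that no method can be precise with so few cases.

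All of this limits the size of the point. It does not supply the missing odds ratio. A P-value alone gives no effect estimate or interval, and the SAP names neither the permutation statistic nor the unit.

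**Conclusion.** The concern holds conditionally. At an assumed prevalence of about 3% or below, an arm with no severe case is at least as likely as not across the whole range of 30 to 60 children per arm, and the planned model has no finite odds ratio for contrasts with it. At higher prevalence the risk falls, though even at 5% only 1.5 to 3 cases per arm are expected, so finite estimates would be very unstable.

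This rests on the assumed prevalence, equal risk in the four arms, and the reading of 30 to 60 analysed children per arm. Household clustering and dropout raise the figures slightly; using more than two children per household would lower them. The primary outcome and the continuous nutrition outcomes are unaffected. The change is worth making because the failure is foreseeable and the remedy is cheap.

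**What to change.** For severe acute malnutrition, amend the SAP to:

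1. Report the number of cases and children in each arm with exact binomial intervals, and state which assessed children are included. If two children per household are counted, note that these intervals ignore household clustering.
2. Replace ordinary logistic regression with Firth-penalised logistic regression, which gives a finite odds ratio when an arm is empty.
3. Take P-values from a permutation test that permutes arm labels across households, using a statistic that stays finite, such as the penalised likelihood ratio. State the household as the unit, since the SAP gives none.

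Using the same method for stunting and moderate acute malnutrition is optional, for consistency.

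The cost is a sentence or two in the SAP and standard software; design, sample size and conduct do not change. The downside is that penalised estimates are slightly shrunk towards no effect and, with this few cases, will still be imprecise.
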